6 STUDY INTERVENTION(S)

6.1 STUDY INTERVENTION(S) ADMINISTRATION

6.1.1 STUDY INTERVENTION DESCRIPTION

SPIRIT Intervention prior to modification:

In its current form, all sessions of SPIRIT are conducted in a private room in a clinic and follow the structured SPIRIT Interview Guide. The goals of SPIRIT are to assist patients to clarify their end-of-life preferences and to help surrogates understand the patient's wishes and prepare for the surrogate role. Currently SPIRIT has two face-to-face sessions with patient and surrogate together. During the first session (~45 min.), an interventionist assesses the patient's and surrogate's cognitive, emotional, and spiritual/religious representations of the patient's illness, progression, and end-of-life care. This allows the interventionist to provide individualized information about topics, such as the effectiveness of life-sustaining treatment for people with progressive chronic illness (to be adapted for AD), and assist the patient to examine his/her values about life-sustaining treatment at the end of life. The interventionist also helps the surrogate prepare for end-of-life decision-making and for the emotional burden of decision-making by actively involving the surrogate in the discussion. If the surrogate is someone out of the order of the hierarchical compensatory model¹⁰⁵ (e.g., a sibling is chosen instead of a spouse or child), the interventionist explores potential family conflicts and encourages the dyad to talk with other family members and complete a medical power of attorney. A Goals-of-Care tool is completed at the end of the session to indicate the patient's preferences. A brief second session (~15 min.) is conducted about 2 weeks later to address remaining or new concerns and questions raised after the first session. The patient's Goals-of-Care tool is reviewed and assessed for the need for clarification or correction. The interventionist documents the patient's end-of-life preferences and the surrogate's name and relationship to the patient in the medical record.

Planned adaptations of SPIRIT

Modification type	Nature of modification
Format/modality	
Virtual face-to-face via web-based videoconferencing for SPIRIT-remote
Setting	
Home for SPIRIT-remote
Content	
Condensing two sessions to one (combining Steps 5 & 6)

	
• Tailoring illness trajectory discussion to AD• Tailoring the likely situations requiring EOL decision making and types of EOL treatment relevant to AD
Delivery process	
• Integrating “enhanced consent techniques”
Training & evaluation	
• Integrating “enhanced consent techniques”• Adding use of videoconferencing for SPIRIT-remote

Guided by Stirman’s framework for adaptations of evidence-based interventions,¹⁰⁶ we have identified modifications that are needed to target patients with mild AD. Drs. [name] and [name] will draft the initial content adaptations and integrate the enhanced consent techniques into the SPIRIT Interview Guide and will work iteratively with Drs. [name], [name], and [name] to complete the initial modifications. The Treatment Fidelity Assessment Tool¹⁰⁷ will also be modified accordingly.

SPIRIT-remote. We will adapt SPIRIT to a videoconference format so that patients and surrogates can receive the intervention in their home. We anticipate SPIRIT delivery via videoconferencing will require minimal training of the interventionist and instructions for participants. The equipment needed for videoconferencing includes a computer, a webcam, a headset, a microphone (if not already built in the computer), and the Internet. We will use Zoom[®], a videoconferencing platform supported in Window, Mac, Linux, and other virtual desktop environments. Zoom also includes a recording module that is consistent with HIPAA security requirements. A videoconferencing workstation will be set up in a private room in the School of Nursing, where the interventionist will conduct sessions.

If a dyad is assigned to the SPIRIT-remote group, a research assistant trained to handle technical aspects of Zoom will schedule a phone call to take the surrogate through the steps of using email to follow URL links that open Zoom. He/she will also guide the surrogate through practice in using basic videoconference operations, e.g., accepting an incoming conference invitation, viewing shared documents, muting/unmuting the microphone or camera, and ending the call. For dyads with a computer without video capabilities, a loaner web cam (and headset and microphone as needed) will be shipped as soon as the group assignment is known. This research assistant will initiate the Zoom call for SPIRIT-remote sessions and silently observe sessions to troubleshoot difficulties the dyad or interventionist might encounter. These procedures have been used effectively in the Tele-Savvy pilot and current R01 project. The interventionist will confirm a follow-up call for outcome assessment to occur in the next 2-3 days ideally.

Usual Care at the Emory ADC. At the time of the diagnosis of a dementing illness, an advanced practice nurse provides written information on advance directives to a patient and his/her family caregiver and reviews this information and encourages them to complete an advanced directive. This typically takes about 10 minutes. Patients and their family members may be referred to attorneys who can assist them in completing an advance directive. If completed, the presence of an advanced directive is documented in the electronic medical record and a copy of the advance directive is scanned to the electronic chart. Patients and families may be referred to a support group program organized by a social worker in which legal and financial issues are discussed in a group setting (by a lawyer). We will review the patient’s medical records at the clinic at baseline and quarterly to track activities associated with usual care. To capture any changes in usual care, policy and procedures related to ACP at the clinic will be reviewed every 6 months by a research assistant.

Usual Care in Emory Geriatrics, Grady’s Marcus Stroke and Neuroscience Center, Grady Geriatrics and Grady Primary Care. At the time of this writing, there are no standardized procedures in place to address the need for advance care planning. Some care providers may encourage patients and/or family caregivers to complete an advanced directive and provide written information during the patient’s clinic visit.

Usual care at Georgia Memory Net by community services educator (CSE). During the second visit of a patient and caregiver at the memory assessment clinic, the CSE asks if the patient has an advance directive, provide written information about advance directives if the patient does not have one, and encourage the patient and caregiver to complete one. This procedure is standardized across the GA Memory Net sites.

Usual care at Rush University's Memory Clinic. Inquiry of completion of legal forms including a living will, POA health care and POA property is done. If incomplete, patients are provided with the forms and may be encouraged to complete before competency comes into question. DNR discussions are typically happening through the PCP, not in our clinic. If someone is truly advanced or at end-stage dementia, discussions about end of life may occur. If a patient or family has more questions, Rush often refers to a social worker for further discussion. A management plan is provided and completion of legal forms is recommended as a part of the management plan.

Usual care at Northwestern University's Memory Clinic.

As applicable (i.e., patients recruited from a clinical care setting), we will review the patient's medical records at the clinic at baseline and quarterly to track activities associated with usual care. For patients without accessible medical records (such as patients receiving care outside of Emory or Grady health systems), study staff will collect medical history from the surrogate decision maker about the patient with dementia. To capture any changes in usual care, policy and procedures related to ACP at the clinic will be reviewed every 6 months by a research assistant.

6.1.2 DOSING AND ADMINISTRATION

Described above (6.1.1).

6.2 PREPARATION/HANDLING/STORAGE/ACCOUNTABILITY

6.3 MEASURES TO MINIMIZE BIAS: RANDOMIZATION AND BLINDING

For Stage 1B pilot testing, [name] (statistician/Co-I) will generate a randomization scheme using stratified (by race, white vs non-white study site, Emory vs Grady), permuted block randomization with block size 6, using a random-number generator. Dyads will be randomized with equal allocation (1:1:1) to SPIRIT-in person, SPIRIT-remote, or usual care.

With Revision 14, randomization will be stratified by race (white vs non-white) within recruitment site (Emory, Rush, and Northwestern), with equal allocation to SPIRIT-in person or usual care.

Due to the nature of the intervention, blinding dyads to their group allocation is impossible, but the research staff assessing outcomes will be blind. Immediately after the completion of the baseline assessment by phone, the data collector will open a sealed envelope to identify group assignment and schedule an intervention session to take place ~2 weeks hence for SPIRIT- in person or –remote (with revision 14, all SPIRIT-remote), as well as a follow-up data collection session in the next 2-3 days.

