Revised study design (V12):

In the effort to meet the target sample size, we expand study recruitment activities to 1) Georgia Memory Net sites (Augusta, Macon, Albany, and Columbus) in addition to Atlanta (Grady memory clinic serves as a memory assessment clinic for GA Memory Net), 2) Atlanta Regional Commission (ARC)/a federally designated Area Agency on Aging (AAA) serving older adults in 10 counties (Cherokee, Clayton, Cobb, DeKalb, Douglas, Fayette, Fulton, Gwinnett, Henry, and Rockdale), and 3) Alzheimer's Association's early stage program (e.g., early stage support groups, monthly lunch groups/Carpe Diem, High Museum tour groups, early memory loss support group series) and referrals to GA Memory Net that covers 33 counties.

Revised study design (V14):

Due to the coronavirus pandemic and social distancing recommendations from CDC, it is necessary to eliminate SPIRIT in-person modality to minimize in-person physical contacts with study participants. This makes the study a 2-group (SPIRIT-remote and usual care) RCT.

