Revised sample size calculation with V14: In light of the changes in study design, we revised our sample size calculation. Moving forward, the new study design will only use a 2-arm (SPIRIT-remote and usual care) RCT for all dyads included in the study based on 3 sites, both within and outside Georgia. Effect sizes estimates, corresponding to the preparedness outcomes from the previous studies, formed the basis for power calculation.^{27-30,32} For dyad congruence, we previously observed large effect sizes ($OR=4.4-8.7$) at 1 or 2 weeks post intervention^{28,32}. We found that a total sample size of 72 obtained by sampling subjects from 3 sites with an average of 12 dyads per group (24 total from each site) will achieve adequate ($>80\%$) power to detect the smallest effect size (odds ratio of 4.3). Because the effect size was negligible for surrogate DMC (Cohen's $d=.02$).³², our goal will be to establish the population parameters. Considering attrition, the target sample size of 120 dyads will achieve sufficient power.

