10.1.8 QUALITY ASSURANCE AND QUALITY CONTROL

All research staff will complete competency-based training for recruitment and data collection activities. The PI and Project Manager will train staff in all study procedures. All project staff will complete university sponsored research integrity training, including modules on the protection of human subjects, HIPAA, and Good Clinical Practice. All roles, responsibilities, and a protocol with scripted subject contacts will be clearly delineated in the study Standard Operating Procedures (SOPs). These SOPs will be easily accessible to the research staff.

Data collectors/recruiters will attend a competency based, one-day training session that the PI and Project Manager will convene. Following a demonstration by the PI or Project Manager on how to recruit participants and obtain informed consent, the recruiters will be expected to perform three satisfactory practice recruitment sessions before actual performance. After demonstrating satisfactory performance of consenting sessions, the recruiters will be authorized to recruit and enroll participants.

Training for data collection will include scripted data collection techniques with special attention to assessing participant fatigue or discomfort during the data collection session. Data collectors will conduct a series of three practice baseline and follow-up data collections using volunteers. After demonstrating satisfactory performance on data collection, they will be authorized to perform data collection activities with enrolled participants. They will also need to demonstrate completeness of data collection activities using REDCap.

The following strategies will be employed for internal quality management of study conduct, data collection, documentation and completion:

- Use of data collection and data entry SOP
- Using paper forms for data collection and then entering data into REDCap
- Use of a second staff member to quality assure data entry between paper and database
- Each data collector signs his/her work
- Audit research staff members' performance (e.g., consenting and data collection) biannually.

We will also employ systematic checking of data quality: The project manager will run quality control checks on the database quarterly during active subject recruitment and data collection; any missing data or data anomalies will be reported to the PI for clarification/resolution.

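### One fixed block size of 6 is printed in the protocol, and staff who see past assignments may also enrol the next dyad; if 6 is kept at 1:1, up to a quarter of assignments can be predicted with certainty.

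*Combined protocol and SAP*

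**What the plan says.** Section 6.3 first describes the three-arm scheme: a stratified list made by the statistician using "permuted block randomization with block size 6", with the allocation rule "Dyads will be randomized with equal allocation (1:1:1) to SPIRIT-in person, SPIRIT-remote, or usual care". The Revision 14 paragraph that follows changes the strata to "stratified by race (white vs non-white) within recruitment site (Emory, Rush, and Northwestern") and the allocation rule to "with equal allocation to SPIRIT-in person or usual care". It mentions neither permuted blocks nor a block size, so 6 is the only value anywhere in the document. Section 4.2 says of V14: "This makes the study a 2-group (SPIRIT-remote and usual care) RCT". The arm named in the V14 sentence of 6.3 is therefore out of step with the design and should be reconciled, but the arithmetic needs only two arms at 1:1.

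On who sees assignments, section 6.3 says that once the telephone baseline is complete "the data collector will open a sealed envelope to identify group assignment" and then books the sessions. No central release is described. On who recruits, section 10.1.8 says "Data collectors/recruiters will attend a competency based, one-day training session". Section 5.5 has the recruiter judge whether the accompanying person is a suitable surrogate, and has Emory staff establish interest and eligibility for candidates referred by Rush and Northwestern.

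**The concern.** A sealed envelope hides the next assignment from view, but it does not stop anyone from deducing it. With one known block size, a person who has seen the earlier assignments in a stratum can sometimes work out the next. Dyads cannot be blinded, so each assignment is known to staff once it is opened.

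Such knowledge matters only if its holder can influence who enters next. Stage 1B leaves some room for that. Staff judge surrogate suitability. They may confirm dementia from other cognitive tests, or from caregiver answers plus an informant questionnaire. Consent and baseline timing are flexible. The primary outcomes (dyad congruence, surrogate confidence, surrogate preparedness) depend on the dyad itself, so a shift in which dyads reach which arm could move the comparison. Modelling baseline values corrects only for measured differences.

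**Working it through.** The plan gives no predictability figure, so there is none to reproduce. The check counts the positions in a block where every remaining slot belongs to one arm, so that the assignment is certain given the earlier ones.

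**Inputs.** Block size 6 (6.3). Two arms at 1:1, so 3/3 per block (6.3 and 4.2, V14); carrying size 6 into V14 is an assumption. Six strata, from 2 race groups × 3 sites (6.3). The 120 dyads come from 9.2 ("the target sample size of 120 dyads will achieve sufficient power"). An even split of 120 / 6 = 20 per stratum, all on the V14 list, is an assumption, because no split is given.

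**Certain assignments, 3/3 blocks.** There are C(6,3) = 20 sequences.
- Positions 1 to 3: never certain.
- Position 4: certain if the first three are alike, 2/20 = 0.1.
- Position 5: certain if the last two are alike, 8/20 = 0.4.
- Position 6: always certain, 1.0.
- Sum: 1.5 of 6 = **25.0%**. The closed form for block size 2k, 1/(k+1), gives 1/4 at k = 3.

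**Incomplete last blocks.** Twenty dyads make three full blocks plus two: 3 × 1.5 + 0 = 4.5 of 20 = **22.5%**, or 27 of 120 over six strata. Three uneven splits, tried as assumptions, gave 20.5% to 23.8%.

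**Best guess (always the lagging arm).** The share correct is [k + (4^k / C(2k,k) − 1)/2] / 2k. At k = 3 this is [3 + (64/20 − 1)/2]/6 = 4.1/6 = **68.3%**, against 50% by chance.

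**Three-arm scheme as written (2/2/2).** There are 90 sequences. Position 5 is certain in 18/90 = 0.2 and position 6 always, so 1.2 of 6 = **20.0%** for the exact arm. For either form of SPIRIT versus usual care, the sum is 1/15 + 3/15 + 7/15 + 1 = 1.733 of 6 = 28.9%.

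**Partial knowledge.** In a 3/3 block, certainty requires having seen all three assignments to the exhausted arm. If one person sees a share p of assignments independently, and knows the block position, the certain share is 0.25 × p³. That is 3.1% at p = 1/2 and 0.9% at p = 1/3. These values of p are assumptions, because staffing is not given.

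**Varying sizes 4, 6 and 8.** This was simulated with 20 dyads per stratum and an observer who knows the set of sizes but not the boundaries. Certain assignments were 2.2% and 2.5% in two separate runs, against about 22% with fixed 6. The lagging-arm guess needs no block size, so it barely changes: expected correct guesses are 2.833 in a block of 4, 4.1 in 6 and 5.329 in 8, and 12.262 / 18 = 68.1%.

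**The case against.** The strongest reply is that several links are inferred. No sentence says that one individual both recruits and opens envelopes. Section 10.1.8 shares a training day but authorises recruiting and data collection separately, and it refers to SOPs that are not in the document. Block size 6 belongs to the superseded 1:1:1 scheme. The 25% needs someone who tracks every assignment in a stratum; with several data collectors each seeing a part, it falls steeply. Envelopes open only after consent and baseline. Rush and Northwestern staff, Memory Net educators and county case managers make first contact for many candidates. Finally, varying the block size leaves the guess rate almost unchanged.

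Most of this stands as a limit on size. It does not remove the opening: nothing forbids the overlap of roles, Emory staff complete screening for all three sites, and 6 is the only block size given.

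A reader might also infer that capacity screening is a route for selection. The document does not support that. Section 5.1 sets a fixed UBACC cut-off of 11 or more for Stage 1B, and consultation on scores of 9 or 10 is described for Stage 1A, which is not randomized. Surrogate choice is also constrained, since the patient chooses and the recruiter works from a guide.

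**Conclusion.** The point holds as a low-cost weakness in allocation concealment. If size 6 is kept at 1:1 and the same staff recruit and open envelopes, up to 25% of assignments in complete blocks are certain to a person who tracks the whole stratum (22.5% under an even split of 120), and the best guess is right up to 68% of the time. Under the scheme as written, the exact arm is certain for 20%. These figures are ceilings.

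It may be tempting to conclude that recruiters do open the envelopes, that a quarter of assignments will be known, or that the comparison will be biased beyond repair. The document shows only that roles may overlap and that prediction is possible. It gives no evidence of misuse and no basis for sizing a bias. The most that can be said is that selection through surrogate suitability, dementia confirmation or timing could bias the result, and that the planned analysis might not fully correct it.

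**What to change.** Generate the remaining V14 list with randomly varying block sizes (for example 4, 6 and 8). The sizes should be known only to the statistician and not stated in the protocol; section 6.3 need say only that they vary and are withheld. The cost is one new list and a line of text. The largest within-stratum imbalance becomes 4 dyads rather than 3.

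Because varying sizes hardly change the guess rate, also keep the running allocations from staff who recruit. Where staffing allows, have existing staff who neither recruit nor assess outcomes release each assignment. This would also ease a tension within the plan: section 6.3 wants outcome assessors blind but has the data collector open the envelope, while section 5.5 prefers to keep the same data collector throughout.

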The most challenging aspects of designing this intervention trial are: a) determining an optimal follow-up time point and data collection mode to minimize the potential influence of patients' cognitive impairment on the outcome assessment, and b) maintaining blinding of data collectors. The first follow-up time point (Ideally 2-3 days post intervention however, consideration is given to difficulty of scheduling dyads and extension may result is to evaluate the impact of SPIRIT on preparedness outcomes while minimizing the potential influence of the patient's impaired ability to recall what was discussed during the SPIRIT session (i.e., the patient needs to recall what he/she clarified as goals-of-care preferences). We considered measuring the outcomes immediately following the intervention, but this would preclude blinding the data collector because of the modality difference. The second follow-up time (12 months post intervention) was chosen to help maximize the number of patients whose conditions progress to an advanced stage within the study period so that we can explore how surrogates experience having or not having an in-depth ACP discussion before the window of opportunity has closed. Although not ideal for people with mild AD, telephone-based data collection was chosen to assure blinding of data collectors and to reduce participants' travel burden. We have used phone-based data collection extensively in our previous studies with seriously ill patients and their surrogates using the procedures described above (see Post-Intervention Assessment).

As in our previous studies, we chose usual care as a comparison condition rather than an attention placebo control. In addition to the fact that there is no methodological standard for attention placebo controls in trials of psychosocial interventions,¹¹⁶ in the context of preparing for future medical care and end-of-life decision making, an attention placebo (information and discussion irrelevant to the context) would not meet the participants' expectations or motivation to participate in the study, and could cause a high refusal rate, dissatisfaction, and disproportional dropouts.¹¹⁶ We will offer SPIRIT-remote to control dyads at the completion of the 1 year follow-up if the patient has not progressed to moderate AD. The same protocol was used in our previous efficacy trial with 12-month follow-ups, and a wait-list control did not result in disproportional dropouts (SPIRIT [5.5%] vs usual care [2.0%]).³⁰

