Because adult day care programs and other community organizations are social services, they typically may not keep health records. In the cases where a dementia diagnosis cannot be confirmed from reliable sources, study staff will administer screening questions and a valid questionnaire, "Short Form of the Informant Questionnaire on Cognitive Decline in the Elderly (Short IQCODE)", to the family caregiver to determine whether a patient's cognitive impairment is likely dementia or due to other neurodegenerative condition. The initial screening questions will consist of the following questions:

- Has your loved one been evaluated for memory problems at the doctor's office?
 - If yes, what was the formal diagnosis at that time?
 - Do you have any test results related to the diagnosis?
- Does your loved one take any cognition- enhancing drugs, such as Aricept, Exelon, Reminyl, Namenda, or Provigil?
- Has your loved one had a stroke before this memory problem?

If a caregiver reports their loved one as having dementia based on the screening question and IQCODE (a score 3.3 or higher), study staff will schedule a meeting to determine full eligibility of their loved one and consent.

For all recruitment sites, the location for consent meeting can be flexible to meet the demands of participants.

Retention strategies:

Stage 1A (pre-testing)

Subject participation will last about three weeks. Each member of the dyad will receive a \$30 gift card at completion of the post-intervention follow-up (Ideally 2-3 days after the intervention session).

Stage 1B (formal pilot testing)

To Maximize Participant Retention, strategies found effective in retaining dyads over 12 months (dropouts, 3.8%) in our efficacy trial³⁰ will be used: (a) obtain backup contact information, (b) make confirmation phone calls 2 days prior to each appointment, (c) make scripted monthly check-in calls, (d) send holiday and special occasion cards, (e) assign the same data collector whenever possible, (f) compensate each member of the dyad as a token of appreciation (\$20 at baseline, \$25 at post-intervention assessment) and surrogates who complete the 1-year follow-up interview (\$30 at 12 months); and (g) use a cell phone matched to the participant's wireless network provider whenever possible (so that their minutes do not run out).

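### The data collector opens the allocation envelope and by default stays with the dyad, so the outcome assessor described as blind will usually know the arm

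*Combined protocol and SAP*

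**What the plan says.** Section 6.3 accepts that dyads cannot be blinded but states that "the research staff assessing outcomes will be blind". The next sentence sets out the randomization step: "the data collector will open a sealed envelope to identify group assignment and schedule an intervention session". This takes place as soon as the baseline call is over, and the same person arranges the outcome call in the same step, described as "as well as a follow-up data collection session in the next 2-3 days". That sentence carries a parenthesis updating it for revision 14, so it is current text.

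Section 5.5 lists, among the Stage 1B retention strategies, the instruction to "assign the same data collector whenever possible".

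Section 4.2 names the blinding of data collectors as one of the two hardest parts of the design. It says that "telephone-based data collection was chosen to assure blinding of data collectors" (and also to spare participants travel), while conceding that the telephone is not ideal for people with mild Alzheimer's disease. It rejects measuring outcomes straight after the session because "this would preclude blinding the data collector because of the modality difference".

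Section 10.1.8 trains a single data-collector role for both baseline and follow-up collection.

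**The concern.** The role that Section 4.2 sets out to keep blind is the role that Section 6.3 has open the envelope. If the same person then makes the post-intervention call, as Section 5.5 prefers, the primary outcomes are collected by someone who knows the arm and booked the SPIRIT session.

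All three primary endpoints in Section 9.1 are self-reports collected by telephone, and the respondents already know their allocation. Dyad congruence is the most exposed. Patients with dementia choose among three options, one of which is being unsure. Two unsure answers count as incongruent, and a dyad must agree on both scenarios to count as congruent (Section 8.1). Repeating a scenario, clarifying it, or accepting a hesitant answer differently by arm can change the binary result. Surrogate confidence and surrogate preparedness are fixed-scale ratings by surrogates alone, so they are less open to prompting, though still given to a listener who knows the arm.

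No later analysis can remove this bias, and a report could not accurately describe the assessment as blinded. The plan would also have accepted telephone collection and a delayed assessment partly for a protection it does not deliver.

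**Working it through.** **Tracing the procedure (Stage 1B).** No figure in the plan bears on this point, so the main check sets the sections side by side.

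1. *Who learns the allocation, and when?* The data collector, immediately after the baseline call (6.3). Baseline answers are unaffected; everything collected later is exposed.
2. *Who books the follow-up assessment?* The same person, in the same step (6.3).
3. *Who makes the follow-up call?* By preference the same data collector (5.5, strategy e).
4. *Which contacts can strategy (e) cover?* The preparedness measures are taken at baseline and post-intervention (8.1). No data are collected between the post-intervention assessment and 12 months (8.3.5). The 12-month record review, confirmatory call and interviews are assigned to a research assistant or interviewer (8.1). The main pair of contacts left for strategy (e) is therefore baseline and post-intervention, which is the pair that unblinds the primary assessment.
5. *Does any section create a separate blinded assessor?* None found. Section 10.1.8 trains one role for both time points. The V5 entry in the amendment history moves outcome measurement from the interventionist to study personnel, but does not separate the envelope-opener from the assessor.

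**Illustration of size.** The documents give no estimate of assessor bias. These inputs are assumptions, apart from the sample size:

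- n = 60 per arm (the target of 120 dyads in 9.2, split equally, with no attrition)
- congruence under usual care p0 = 0.40 (assumed)
- no true effect; assessor-induced shift d in the SPIRIT arm of 0.05, 0.10 or 0.15 (assumed)
- two-sided 5% test of two proportions, normal approximation

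Formulas, with p1 = p0 + d and p̄ = (p0 + p1)/2:

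- OR = [p1/(1 − p1)] / [p0/(1 − p0)]
- SE0 = √[2p̄(1 − p̄)/n]; SE1 = √{[p0(1 − p0) + p1(1 − p1)]/n}
- P(reject) = 1 − Φ[(1.96·SE0 − d)/SE1] + Φ[(−1.96·SE0 − d)/SE1]

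| d | p1 | Spurious OR | SE0 | SE1 | P(reject) |
|---|---|---|---|---|---|
| 0.05 | 0.45 | 0.8182/0.6667 = 1.23 | 0.0903 | 0.0901 | 0.0796 + 0.0059 = 0.086 |
| 0.10 | 0.50 | 1.0000/0.6667 = 1.50 | 0.0908 | 0.0904 | 0.1940 + 0.0010 = 0.195 |
| 0.15 | 0.55 | 1.2222/0.6667 = 1.83 | 0.0912 | 0.0901 | 0.3751 + 0.0001 = 0.375 |

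With the 72 dyads (36 per arm) that Section 9.2 says give adequate power, the odds ratios are unchanged and the same formula gives 0.071, 0.135 and 0.245.

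For scale, the full-scale dialysis trial in Section 2.2 reported OR 1.89 over 2 to 12 months. The present trial is sized on larger short-term effects: OR 4.4 to 8.7 in earlier studies, with 4.3 as the smallest effect in the V14 calculation.

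**The case against.** The strongest reply is that no sentence says the envelope-opener makes the follow-up call. Section 6.3 says only that this person schedules it, and Section 5.5 is qualified by possibility. Where blinding is required, keeping the same collector could be read as not possible. Section 10.1.8 also defers roles and scripted contacts to operating procedures that are not part of the documents, and these may separate the two tasks. All of this limits what can be said about actual conduct: some dyads may be assessed by a blind collector. It does not give a reading in which the written procedure protects the assessor. The blinding commitment has no mechanism behind it, and the text points the other way.

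Other points stand as limits on the argument. Only dyad congruence uses patient answers and the unsure option. Data collection is scripted, which restrains prompting. Blinding was not the only reason for telephone collection. The size calculation uses an assumed control rate and assumed shifts in a simple two-proportion test, whereas Section 9.4.2 plans a mixed model with a treatment-by-time interaction. The spurious odds ratios are also well below the short-term effects on which the trial is sized.

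Finally, this is a Stage I pilot seeking preliminary efficacy. That lowers the stakes of a false positive, but Section 9.1 still tests all three endpoints for significance.

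**Conclusion.** The point holds: the text is wrong as written. Followed literally, Sections 6.3 and 5.5 make an unblinded post-intervention assessment the default for all three primary endpoints, contrary to the commitment in 6.3 and the rationale in 4.2. This rests on the wording alone and needs no calculation.

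The size of any bias is unknown. Under the assumptions shown, a shift of 5 to 15 points in congruence would produce an odds ratio of 1.23 to 1.83 from no effect, and would raise the false-positive rate from 5% to between about 9% and 38% with 60 dyads per arm. These figures show sensitivity and are not a forecast. The matter should be settled before further outcome data are collected, because it touches every primary endpoint and cannot be corrected afterwards.

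**What to change.** - **Section 6.3:** have a named staff member who collects no post-randomization outcomes open the envelope and book both the SPIRIT session and the follow-up call. The research assistant who already telephones SPIRIT dyads about Zoom (6.1.1) could do this, provided that person assesses no outcomes. The project director is a less clean choice, because Section 10.1.7 gives that role a review of primary endpoint data.
- **Section 6.3:** state that the post-intervention assessment is made by a data collector who has not seen the allocation and made no scheduling calls. Section 8.1 times this assessment from the intervention or from randomization, so the appointment list given to the collector should not show the baseline date.
- **Section 5.5, strategy (e):** limit it to contacts that collect no post-randomization outcomes.
- **Residual unblinding:** dyads may still reveal their arm. Ask them at the start of the call not to do so, and record the collector's guess of allocation after the primary measures and before the acceptability questions, which refer to SPIRIT sessions.

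The cost is protocol and procedure wording plus reassignment of one existing task, with no new staff. Some dyads will hear a different voice at follow-up. If the separation cannot be made, remove the statement that assessors are blind and report the assessment as unblinded.
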